1. INTRODUCTION AND RATIONALE

Yearly, around 6000 patients in the Netherlands suffer from cardiogenic shock (CS) due to acute myocardial infarction (AMI) and this number will only increase, based on demographic developments.[1] Despite efforts to improve survival mortality in CS is as high as 50% and the only evidence based therapy is early revascularization. [2-5] CS after AMI results from the loss of myocardial cells due to ischemia. The poor pumping function of the heart leads to a state with low blood flow to end-organs resulting in multi-organ failure and high mortality rates. Renal failure (and subsequent renal replacement therapy) occurs due to decreased perfusion of the kidneys and is a surrogate marker for end-organ perfusion and a strong predictor for death in CS.[6]

The first-line pharmacologic strategy in CS is noradrenaline, as recommended by current scientific statements.[2, 7] Noradrenaline is a vasopressor drug routinely used in the treatment of CS, under the assumption that a higher mean arterial blood pressure (MAP) will improve myocardial and other end-organ (e.g. renal) perfusion. However, there is no evidence that noradrenaline use and higher blood pressures improve patient outcomes. Firstly, pharmacologically induced improvement of blood pressure has not been associated with better survival. Secondly, there is no evidence that an increase in MAP, if achieved by noradrenaline, leads to greater myocardial and other end-organ blood flow. As a matter of fact, its vasoconstrictive properties reduce flow to the microcirculation of the myocardium and organs, as can be frequently seen by discolouring of skin in patients treated with noradrenaline.[8, 9] And lastly, noradrenaline is associated with adverse events such as (supra-)ventricular arrhythmias that reduce the efficacy of the myocardial pumping function and increase the myocardial oxygen demand. This can lead to expansion of infarct size and worsening of the heart muscle function.

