7.1.3 Laboratory data

The following laboratory data, that are part of routine care unless stated otherwise, are entered into the eCRF (*for details, see table 2*):

- Cardiac enzymes: serial measurements during the first 72 hours for hs-troponine T and CK-MB*.
- Lactate: will be measured at baseline, at 3 and 6 hours after randomization and with larger intervals hereafter.
- Creatinine: serial creatinine-levels during ICU / CCU stay, level at one year
- Other: C-reactive protein, glucose, hemoglobin, leukocytes, nt-proBNP* and blood urea nitrogen will be measured on admission and daily during ICU/CCU stay.

* Not part of routine care in every hospital

	T = 0 (ICU admission)	T = 3	T = 6	T = 12	T = 24	Day 2	Day 3	Day 4
Lactate	X	X	X	X	X	X	X	X
Hb	X				X	X	X	X
Leukocytes	X				X	X	X	X
CRP	X				X	X	X	X
Glucose	X							
Creatinin	X				X	X	X	X
Blood urea nitrogen	X				X	X	X	X
Liver function	X				X	X	X	X
Troponine T(hs)	X		X	X	X		X	
CK-MB	X		X	X	X		X	
Nt-proBNP	X					X		
Hourly blood pressure and heart rate for the first 24h	X	X	X	X	X			
Invasive haemodynamic measurements	X		X	X	X	X		
Urine production					X	X	X	X
Echocardiography							X	
ECG	X		X		X	X	X	X

Table 2.

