8.3 Tertiary endpoints *(for definitions, see Appendix A)*

The tertiary endpoints are:

- Days alive and out of ICU (30 days)
- Cardiovascular death at 1 year
- Enzymatic infarct size
- Lactate clearance (mean + area under the curve 0-36 hours)
- Days alive and free of mechanical ventilation (30 days)
- Days alive and free of mechanical circulatory support (30 days)
- Severe renal failure requiring renal replacement therapy (at 30 days, 1 year)
- Renal function (during hospital stay and 1 year)
- Time to peak creatinine (hospital stay)
- Time to renal replacement therapy
- Days alive and free of catecholamine therapy (30 days)
- Vasoactive inotropic score (VIS) (during hospital stay)
- Time to hemodynamic stabilization (hospital stay)
- Blood pressure and heart rate during the first 24 hours
- Hemodynamic parameters (during ICU / CCU admission)
- Arrhythmias during hospital admission
- Major vascular complication during admission (bleed or thrombo embolic event)
- Infection / sepsis during hospital admission
- Myocardial re-infarction within 30 days
- Left ventricular ejection fraction (at day 3, before hospital discharge, and at 1 year)

- Neurological outcome (at 30 days and 1 year)
- Protocol adherence / use of bail-out therapy
- Hospital readmission for cardiac reason within 1 year

The cost-effectiveness endpoints are:

- Health-related quality of life based on the EQ-5D-5L questionnaire at 12 months
- Resource utilization based on iMTA Medical Consumption (iMCQ) and iMTA Productivity Cost Questionnaire (iPCQ) (at 30-day, 3-month, 6-month and 1-year follow-up)

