9.3 Determination of sample size

The rate of the primary endpoint in the reference group was estimated from the culprit-shock trial, where the event rate was 45.9%.[3] No other study ever tested the same intervention but from experimental myocardial infarction studies we have learned that the administration of noradrenaline is associated with infarct size expansion up to 22%.[12] Besides that, patients with high noradrenaline levels after myocardial infarction have a 4 times higher mortality rate compared with those without high noradrenaline levels.[13] On the basis of the much higher death rate and larger infarct size, we hypothesize that the event rate of the primary endpoint under the lower MAP-target regimen might be 10% lower than that under the standard MAP-target regimen. These assumptions form the basis for the sample size calculation for superiority testing of the primary endpoint. For non-inferiority testing we took a non-inferiority margin of 10%, equivalent to the inverse of the above mentioned treatment benefit.

We calculated that with 752 evaluable patients, the study has 80% power to show superiority of the lower MAP-target regimen (versus the standard MAP-target regimen) under the above mentioned design assumptions, with rates of the primary endpoint of 45.9% under the standard MAP-target regimen and of 35.9% under the lower MAP-target regimen.

We further calculated that with 752 evaluable patients, the study has 79% power to show non-inferiority of the lower MAP-target regimen (versus the standard MAP-target regimen) with a non-inferiority margin of 10% and event rates of the primary endpoint of 45.9% in both treatment regimens.

To allow for attrition rate of 3%, 776 (2 x 388) patients will be randomized.

Sample size calculation is made using PASS Sample Size Software, version 13.

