Unchanged	Residual ST-segment elevation of 70% or more of that on the first ECG (no ST-segment elevation resolution)

Classification of death (ARC-2 definition)	
Type	Definition
Cardiovascular death	Death resulting from cardiovascular causes. The following categories may be collected: 
 • Death caused by acute myocardial infarction • Death caused by sudden cardiac, including unwitnessed, death • Death resulting from heart failure • Death caused by stroke • Death caused by cardiovascular procedures • Death resulting from cardiovascular hemorrhage • Death resulting from other cardiovascular cause
Non-cardiovascular death	Death that is not thought to be the result of a cardiovascular cause. The following categories may be collected: 
 • Death resulting from malignancy • Death resulting from pulmonary causes • Death caused by infection (includes sepsis) • Death resulting from gastrointestinal causes • Death resulting from accident/trauma • Death caused by other non-cardiovascular organ failure 
Death resulting from other non-cardiovascular cause

Undetermined	Undetermined cause of death is defined as a death not attributable to any other category because of the absence of any relevant source documents. Such deaths will be classified as cardiovascular for end point determination.

Renal failure requiring renal replacement therapy

Any indication for renal replacement therapy (both temporary and permanent) such as dialysis, hemofiltration or hemodiafiltration such as renal failure with one of the following criteria:

- Otherwise untreatable volume overload
- Hyperpotassemia
- Severe uremia
- Persistent severe metabolic acidosis

Enzymatic infarct size

Type	Definition
Peak-value	Highest levels of hs-troponin-T (hs-cTnT) (ng/l) and creatinine-kinase myocardial band (CK-MB) ($\mu\text{g/L}$) as measured during the index admission and within 3 days after the PCI.
Area under the curve	Area under the curve until 72 hours for hs-troponin-T (hs-cTnT) (ng/l) and creatinine-kinase myocardial band (CK-MB). Missing data from patients who died before 72 hours will be imputed according to the worst case scenario (i.e., the missing value will be replaced with the highest hs-cTnT / CK-MB in the corresponding treatment group).

Lactate clearance

Mean value and area under the curve until 36 hours, in mmol/L.

Days alive and out of hospital (DAOH)

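### The two versions of enzymatic infarct size treat death before 72 hours inconsistently, so unequal early death pulls peak and AUC in opposite directions

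*Protocol*

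**What the plan says.** Protocol section 8.3 lists "Enzymatic infarct size" once among the tertiary endpoints and refers to Appendix A for its definition. Appendix A gives two rows under that name.

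- **Peak value:** the highest hs-troponin-T and CK-MB "as measured during the index admission and within 3 days after the PCI". Nothing is said about death or missing samples.
- **AUC until 72 hours:** "Missing data from patients who died before 72 hours will be imputed according to the worst case scenario", which is spelled out as "the missing value will be replaced with the highest hs-cTnT / CK-MB in the corresponding treatment group".

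Section 7.1.3 calls for "serial measurements during the first 72 hours for hs-troponine T and CK-MB", and its Table 2 marks the enzyme samples at 0, 6, 12 and 24 hours and on day 3. Section 9.4 leaves the analysis of tertiary endpoints to the SAP. No other part of the protocol gives the peak a death rule or says which version is the endpoint.

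**The concern.** The protocol recognises that early death interrupts the enzyme curve, but deals with it in one row only. Take a patient who dies before the highest sample. Under the peak row that patient is scored on a rising curve, which is too low. Under the AUC row the samples after death are filled with the arm's highest value, which is very high. One death therefore counts as a smaller infarct in one version and a larger infarct in the other.

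The AUC rule has a second weakness. The fill-in value is specific to the treatment group, so a death in one arm may carry a different penalty from a death in the other.

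Early death is unlikely to be rare here. Section 1 states that "mortality in CS is as high as 50" percent, and the trial is designed to find a difference in an endpoint that includes death. If the lower target works, fewer early index deaths make the index arm look worse on peak and better on AUC. If it harms, the reverse holds. Infarct expansion is part of the trial's stated rationale, so two infarct-size results that disagree for this reason would be hard to interpret.

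**Working it through.** **Side by side**

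| Patient | Peak row | AUC row |
|---|---|---|
| Survives 72 h | highest measured value | area from measured values |
| Dies before 72 h, after the highest sample | true sampled peak is kept | later samples filled with own arm's highest value |
| Dies before the highest sample | truncated, too low | later samples filled with own arm's highest value |

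The rows conflict most in the third line.

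**Inputs from the protocol.** 388 per arm (section 9.3: "776 (2 x 388) patients will be randomized"); samples at 0, 6, 12, 24 and 72 h (Table 2, with day 3 taken as 72 h); the two definitions as written.

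**Assumed, because the protocol gives no figures.** Early death of 5% to 15% per arm, spread evenly over 0–24 h or 0–72 h and independent of infarct size; log-normal peak with log SD 0.8; median time to peak of 8, 14 or 20 h. The baseline sample is always available. There is no true difference in infarct size. Each scenario was run 400 times.

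**Measure.** The Mann-Whitney probability P that an index patient has a larger value than a reference patient; 0.50 means no difference. Its null standard error is √[(388 + 388 + 1) / (12 × 388 × 388)] = 0.0207. The Monte Carlo error of each mean is about 0.0207/√400 = 0.001.

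**Results.** Ranges run over the three times to peak. For AUC they also cover two readings of the fill-in value: the arm's highest at that time point, or at any time. Opposite signs are counted under the first reading.

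| Early death, index v reference | Deaths within | P, peak | P, AUC | Opposite signs |
|---|---|---|---|---|
| 5% v 15% | 24 h | 0.513–0.519 | 0.449–0.452 | 71–78% |
| 5% v 15% | 72 h | 0.503–0.507 | 0.449–0.477 | 42–59% |
| 10% v 15% | 24 h | 0.506–0.509 | 0.474–0.476 | 46–56% |
| 10% v 15% | 72 h | 0.502–0.504 | 0.474–0.488 | 28–49% |
| 15% v 10% | 24 h | 0.489–0.495 | 0.523–0.527 | 51–59% |
| 15% v 10% | 72 h | 0.495–0.498 | 0.510–0.524 | 32–40% |
| 10% v 10% | 24 h | 0.499–0.502 | 0.500–0.502 | 26–27% |
| 10% v 10% | 72 h | 0.500–0.501 | 0.499–0.501 | 18–22% |

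With equal early death both versions centre on 0.50, and opposite signs occur by chance in 18–27% of trials. Whenever early death is unequal, the two means lie on opposite sides of 0.50.

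**Size in standard errors, 5% v 15%**

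- Peak, deaths within 24 h: 0.013/0.0207 = 0.6 to 0.019/0.0207 = 0.9.
- Peak, deaths over 72 h: 0.003/0.0207 = 0.1 to 0.007/0.0207 = 0.3.
- AUC: 0.023/0.0207 = 1.1 to 0.051/0.0207 = 2.5.

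**How many early deaths are truncated.** 31–81% if deaths fall within 24 h, and 10–27% if they spread over 72 h. The rest keep their sampled peak.

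**What a common worst rank would do.** If every death before 72 h shares the worst rank in both arms, and survivors do not differ, then P = 0.5 + (index death rate − reference death rate)/2. For 5% v 15% this is 0.5 − 0.05 = 0.45; for 10% v 15% it is 0.475. Peak and AUC then give the same expected answer. These values are close to what the AUC rule already produces in most scenarios, so the fix mainly brings peak into line and removes the arm-specific penalty.

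**The case against.** The strongest reply is that little is at stake. Infarct size is one of 23 tertiary endpoints in section 8.3, outside the four-step hierarchy of section 9.2, with no success criterion attached. Both versions are prespecified, and reporting two summaries of one curve is not an error. The peak row states no wrong death rule; it is silent, and section 9.4 sends tertiary analyses to an SAP that is not at hand. Most of this stands and limits the weight of the point. It does not remove it: the protocol itself fixes the AUC imputation and confines peak to measured values, so the two rows conflict if followed as written.

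A reader might go further and infer that peak alone could yield a false finding of smaller infarcts. That needs every early death to be seen at only 5% to 50% of its eventual peak. The mean log reduction over that range is 1.44. Early death of 10% v 15% then shifts the log mean by 0.05 × 1.44 = 0.072, about 1.1 standard errors (SE 0.067). Early death of 10% v 20% shifts it by 0.144, roughly 2.1. The sampling schedule does not support this, because a patient who dies on day 2 can already have four samples. With the truncated shares above, the shifts fall to about 0.1–0.9 and 0.2–1.7 standard errors. A 10-point gap in death before 72 h would also equal the whole 30-day difference assumed for the primary composite in section 9.3.

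Nor is it right that the largest fatal infarcts are generally recorded as small by peak. That applies only to deaths before the highest sample, and a very large infarct may already read high at 6 or 12 hours.

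**Conclusion.** The point holds as an inconsistency of definition with modest numerical consequences. Appendix A treats death before 72 hours in two incompatible ways within one endpoint, and unequal early death then separates the two results even when infarct size is the same. For 5% v 15% early death the pull on peak is at most about 0.02 in Mann-Whitney probability, under 1 standard error; the opposite shift in AUC is larger, up to about 0.05. At 10% v 15% the shifts are below 0.01 and up to about 0.026.

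These sizes rest on assumed shares and timing of early death, an assumed curve shape, and death unrelated to infarct size. The direction of the conflict follows from the text. The documents do not support the inference that peak alone would produce a false claim. The primary and ranked secondary conclusions are unaffected. It should be corrected because doing so is cheap, ideally before any data by arm are seen.

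**What to change.** Put one death rule in Appendix A for both rows and both arms. For example, give every patient who dies before 72 hours a common worst rank for peak and for AUC, and compare the arms by a rank test in all randomised patients. This replaces the fill-in with the arm's own highest value. State the time origin of the 72 hours, so that the same patients fall under the rule in both rows. Name one version as the infarct-size endpoint and the other as supportive, and report the results from observed values as a sensitivity analysis.

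This costs definition wording only; no new samples or visits are needed. The downside is that the endpoint then partly measures early death, including deaths not caused by infarct size: with 5% v 15% early death, P is 0.45 even if infarct size is identical. The report should say so, and the observed-values analysis should be read beside it, with the caution that it keeps the truncated peaks.

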3. STUDY DESIGN

An open label, multicenter randomized controlled trial to ensure level 1 evidence for superiority of the intervention. The standardcare arm will provide a reliable basis for the cost-effectiveness analysis. Patients will be randomly assigned (1:1) to the index regimen (lower MAP-target of ≥ 55 mmHg) or reference regimen (standard MAP-target of ≥ 65 mmHg). Inclusion is estimated to take three years (36 months).

[figure not shown]

Figure 1.

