9.2 Main analysis of the primary endpoint and ranked secondary endpoints

The following hypotheses are tested in a hierarchical order, to preserve type I error rate:

1. A lower MAP-target regimen (≥ 55 mmHg) is non-inferior to the standard MAP-target regimen ($\text{MAP} \geq 65$ mmHg) in terms of the primary endpoint of the composite of all-cause mortality and severe renal failure at 30 days.
2. A lower MAP-target regimen (≥ 55 mmHg) is superior to the standard MAP-target regimen ($\text{MAP} \geq 65$ mmHg) in terms of the primary endpoint of the composite of all-cause mortality and severe renal failure at 30 days.
3. A lower MAP-target regimen (≥ 55 mmHg) is superior to the standard MAP-target regimen ($\text{MAP} \geq 65$ mmHg) in terms of the first secondary endpoint of all-cause mortality at 30 days.
4. A lower MAP-target regimen (≥ 55 mmHg) is superior to the standard MAP-target regimen ($\text{MAP} \geq 65$ mmHg) in terms of the second secondary endpoint of days alive and out of hospital at 30 days.

All analyses are performed on an intention-to-treat (ITT) basis. The ITT population consists of all subjects who have been randomized (i.e. when the subject number and allocated regimen are recorded in the electronic case report form (eCRF)). Patients are analysed in accordance with the randomized treatment assignment irrespective of the factual implementation of the assigned treatment regimen.

Rates of primary and first secondary endpoint are estimated as the cumulative incidence at 30 days after randomization by the Kaplan-Meier method. Rate differences are defined as the rate in the index group minus the rate in the reference group.

1. Non-inferiority of the lower MAP-target regimen in terms of combined all-cause mortality and severe renal failure at 30 days is declared if the upper limit of the 95% confidence interval (CI) of the rate difference excludes 10%. This is the equivalent of non-inferiority testing with a one-sided alpha of 0.025 with a non-inferiority limit of 10%.
2. Superiority of the lower MAP-target regimen in terms of combined all-cause mortality and severe renal failure at 30 days is declared if the 95% confidence interval (CI) of the rate difference excludes 0%. This is the equivalent of superiority testing with a 2-sided alpha of 0.05.

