9.4 Tertiary analyses

The statistical analyses of the tertiary endpoints will be described in the statistical analysis plan.

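### The infarct-size AUC gives early deaths the maximum of their own arm, so chance differences between two single values enter the comparison

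*Protocol*

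**What the plan says.** Protocol section 8.3 lists "Enzymatic infarct size" among the tertiary endpoints. Appendix A defines it in two ways: the peak hs-troponin-T and CK-MB within 3 days of PCI, and the AUC of each to 72 hours. Only the AUC entry carries an imputation rule: "Missing data from patients who died before 72 hours will be imputed according to the worst case scenario". The rule then says what that means: "the missing value will be replaced with the highest hs-cTnT / CK-MB in the corresponding treatment group".

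Section 9.4 leaves the tests to a later document: "The statistical analyses of the tertiary endpoints will be described in the statistical analysis plan". The imputation rule is not deferred in this way. Appendix A fixes it.

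**The concern.** A worst-case rule is meant to score the same bad outcome in the same way. Here the outcome, death before 72 hours, is scored by allocation. Each arm has its own worst value, and that value is the arm's single largest observation. Enzyme values are usually right-skewed, so two sample maxima can differ noticeably by chance even when the arms have the same distribution. The whole block of early deaths in one arm is then shifted against the block in the other. An ordinary standard error treats the imputed values as independent observations and does not allow for the chance variation in the maximum that they all share.

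A rank test is not immune. If whole AUCs are imputed, every early death in the arm with the larger maximum outranks every early death in the other arm.

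What is at stake is how a mechanistic result is read. Infarct expansion under noradrenaline is part of the rationale (section 1) and part of the case for the assumed effect (section 9.3). A spurious difference in either direction could be taken as support for that mechanism or as evidence against it.

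**Working it through.** **Inputs from the protocol.** The plan states no figure for this endpoint, so only the arm size can be reproduced. Section 9.3: "To allow for attrition rate of 3%, 776 (2 x 388) patients will be randomized". Check: 752 / 0.97 = 775.3, rounded up to 776, which is 388 per arm.

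**Assumptions (not in the protocol).**
- Share dying before 72 h, equal in both arms: 5%, 10%, 20% or 30%.
- Enzyme distribution: lognormal, log-SD 0.5, 1.0 or 1.5.
- Two-sided 5% level, borrowed from the superiority tests in section 9.2.
- Test: Welch t on raw values, Welch t on logs, or Mann-Whitney.

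**Two readings of the missing value.** (A) The whole AUC of an early death is replaced by the own-arm maximum. (B) Each sample missing after death is replaced by the own-arm maximum at that time (0, 6, 12, 24, 72 h), and the AUC is then computed by the trapezoid rule.

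**Hand check, reading A, Mann-Whitney.** With early-death share d in each arm, a shared worst value would leave the two blocks tied and contribute d²/2 to the probability that one arm exceeds the other. With separate maxima one block wins outright and contributes d². The shift is d²/2. The null standard error is √[(2n+1)/(12n²)] = √[777/(12 × 388²)] = 0.0207. The rejection probability is P(Z > 1.96 − s) + P(Z < −1.96 − s), where s is the shift divided by 0.0207.

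| d | shift d²/2 | s | approximate rejection |
|---|---|---|---|
| 5% | 0.00125 | 0.06 | 5.0% |
| 10% | 0.005 | 0.24 | 5.7% |
| 20% | 0.020 | 0.96 | 16% |
| 30% | 0.045 | 2.17 | 58% |

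This is slightly low, because it ignores survivors in one arm who exceed the other arm's maximum. It also shows why the problem is small at low d: the shift grows with d².

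**Simulation under no effect.** 3,000 trials per scenario, 388 per arm, log-SD 1, own-arm maximum. Entries are the percentage of trials rejecting at nominal 5%.

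| Early deaths | A: raw t | A: log t | A: Mann-Whitney | B: raw t | B: log t | B: Mann-Whitney |
|---|---|---|---|---|---|---|
| 5% | 32.6 | 6.4 | 5.1 | 19.2 | 6.5 | 5.3 |
| 10% | 47.6 | 10.2 | 6.0 | 32.3 | 10.4 | 6.8 |
| 20% | 62.0 | 18.3 | 18.5 | 46.8 | 18.3 | 12.1 |
| 30% | 70.5 | 27.9 | 61.6 | 55.2 | 25.4 | 23.0 |

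The simulation error at a true 5% is √(0.05 × 0.95 / 3000) = 0.4 percentage points. Further runs at log-SD 1 gave Mann-Whitney rates of 11–20% at 20% early deaths and 25–64% at 30%, and raw t rates up to 34% at 5% and 46–63% at 20%. The ranges quoted elsewhere cover all these runs.

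**Other skewness.** For log-SD 0.5 to 1.5, Mann-Whitney under A stays at 18.5–19.0% (20% early deaths) and 61.6–62.8% (30%), as it must, since only ranks matter. Under B it is 9.5–12.6% and 17.2–26.8%. The raw t-test is more sensitive: at 5% early deaths it runs from 17.7% to 47.0% (A) and from 9.4% to 31.3% (B).

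**With one common maximum for both arms.** Rejection is 4.3–6.0% over all 72 combinations (4 shares × 3 log-SDs × 2 readings × 3 tests), which is nominal within simulation error.

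**The case against.** The strongest reply concerns scope and size, and much of it stands.

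- **Scope.** A reader might infer that the trial's type I error is inflated. The documents do not support that. Section 9.2 sets a hierarchy of four hypotheses, and infarct size is in none of them. A reader might also take the whole infarct-size endpoint to be affected, but the rule sits only under the AUC.
- **No test is fixed.** The large t-test figures assume an analysis that the protocol does not choose. Section 9.1 summarizes skewed variables by medians, and section 9.2 uses Mann-Whitney for days alive and out of hospital, so a rank test is at least as likely here.
- **Early-death share.** At 10% or less, Mann-Whitney is close to nominal. Against the section 9.3 composite rates of 45.9% and 35.9%, a 20% share would be 20/45.9 = 44% and 20/35.9 = 56% of all 30-day events. A 30% share would be 65% and 84%. The 30% row is an extreme case.
- **Reading of the rule.** The wording names an enzyme level, which fits reading B better, and B gives the smaller Mann-Whitney rates at 20% and 30%.
- **Constant value.** It is tempting to say that imputing a constant is itself the fault because it adds no variance. The common worst value is also a constant, yet it keeps the nominal rate. The fault is having a different constant in each arm.

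None of this defends the arm-specific maximum. The protocol fixes it, gives no reason for it, and a shared value serves the same worst-case purpose without the side effect.

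**Conclusion.** The point holds for the AUC definition of a tertiary endpoint and no further. The rule scores the same outcome differently by arm and lets the chance gap between two maxima enter the comparison.

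The size depends on two things the protocol does not give. With Mann-Whitney, the null rejection rate is about 5–7% at 5–10% early deaths, 11–20% at 20% and 23–64% at 30%. With a raw-scale t-test it is about 19–34% already at 5% early deaths and 46–63% at 20%. These figures assume lognormal values with log-SD 1, 388 per arm, equal early mortality and a two-sided 5% level, and they span both readings of the rule. If early deaths are few and the SAP uses a rank test, the practical effect is negligible. Otherwise it can be large. The primary and ranked secondary conclusions do not depend on it.

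**What to change.** In the AUC entry of Appendix A, take the replacement value from both arms combined instead of the patient's own arm, or give all deaths before 72 hours one shared worst rank. State in the same sentence whether the value replaced is the individual missing sample or the whole AUC. Preferably have the SAP compare the arms with a rank-based test, which also limits the influence of the single largest value on the result.

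Early death still counts as the worst outcome, as the rule intends. The cost is one sentence in Appendix A and matching text in the SAP. No new data and no change to sample size are needed. The change should be made before any comparison of enzyme data by arm.

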4.3 Inclusion criteria

In order to be eligible to participate in this study, a subject must meet all of the following criteria:

1. Acute myocardial infarction, STEMI or NSTEMI
2. Cardiogenic shock, characterized by:
 - I. Signs of impaired organ perfusion with at least one of the following criteria:
 - a. Altered mental status
 - b. Cold, clammy skin and extremities
 - c. Oliguria with urine output < 30ml/hour
 - d. Serum lactate > 2.0 mmol/L
 - II.
 - a. Systolic blood pressure (SBP) < 90 mmHg for > 30 minutes, OR
 - b. Use of drugs to maintain SBP > 90 mmHg at presentation before randomization.
 - III. Signs of pulmonary congestion

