5.4 Use of co-interventions

The use of other vasoactive medication is allowed under strict regulations. Patients need to have some sign of clinical deterioration, e.g. a decrease in urinary output, mottling of the skin or an altered mental status. This observation should be confirmed biochemically by measurement of lactate. If lactate is ≥ 2 mmol/L or higher than baseline measurement, patients are observed 2-4 hours before lactate measurement is repeated. If lactate fails to drop after this observational period, a hemodynamic profile is obtained, preferably via a pulmonary artery catheter. If invasive hemodynamic measurement indicates a poor cardiac output, physicians may consider adding inotropes. If lactate still fails to drop with this new strategy, further treatment is left at the discretion of the treating physician. This includes letting go of the MAP-target and starting any medication. The steps mentioned above are summarized in **figure 2**.

The use of mechanical circulatory support devices, such as Impella, IABP and ECMO, is allowed under strict criteria when bail-out therapy is necessary. That is when medical therapy fails (persistently high lactate, poor cardiac output) despite treatment according to the medical guidance protocol (usually on very high vasoactive treatment).

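### The tertiary endpoint named lactate clearance has no baseline term, so it measures lactate exposure; its AUC unit, 36 h window and handling of early deaths also need correcting

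*Protocol*

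**What the plan says.** Protocol section 8.3 lists lactate clearance among the tertiary endpoints, as a mean plus an area under the curve over 0 to 36 hours, and refers to Appendix A for definitions. The whole Appendix A entry is: "Mean value and area under the curve until 36 hours, in mmol/L".

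Section 7.1.3 says that lactate "will be measured at baseline, at 3 and 6 hours after randomization and with larger intervals hereafter". Table 2 lists lactate at T = 0, 3, 6, 12 and 24, then on Days 2, 3 and 4. It labels T = 0 as ICU admission, whereas the text counts from randomization.

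The Appendix A entry just above lactate, the AUC for enzymatic infarct size, has a rule for early deaths: "Missing data from patients who died before 72 hours will be imputed according to the worst case scenario". The lactate entry has no such rule.

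On analysis, section 9.4 says: "The statistical analyses of the tertiary endpoints will be described in the statistical analysis plan".

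**The concern.** Clearance means a fall from a starting value. The definition contains no baseline value, change, percentage or slope, although a baseline sample is taken. The protocol treats change as the informative signal elsewhere. In section 5.4 the next step in a deteriorating patient depends on the trend: "If lactate fails to drop after this observational period, a hemodynamic profile is obtained".

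The stake is interpretation. The trial tests whether a lower MAP target can be used, and lactate is one of its perfusion markers. A result reported as better lactate clearance would be read as preserved or improved perfusion. A mean or AUC of the level cannot support that statement, because a patient who enters with low lactate and never improves scores well.

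Three details of the same entry add to this: a unit that cannot apply to an AUC, a window that ends where no sample is scheduled, and no rule for patients who die inside the window.

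**Working it through.** The protocol gives no figure for this endpoint, so there is none to reproduce. The check applies the stated definition to assumed lactate profiles (mmol/L) at 0, 3, 6, 12, 24 and 36 h. The times up to 24 h are from Table 2. The 36 h value is assumed, since Table 2 has none.

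Formulas:
- AUC = sum over intervals of (interval length) × (average of the two end values), in mmol·h/L.
- Sample mean = sum of the values / number of samples.
- Time-weighted mean = AUC / 36 h.
- Clearance = (value at 0 h − value at 36 h) / value at 0 h.

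**Does the definition rank patients by clearance?**

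- A, falling (10, 8.5, 7, 5, 3, 2): AUC = 27.75 + 23.25 + 36 + 48 + 30 = 165.
- B, flat at 3.0: AUC = 3 × 36 = 108.
- C, worsening (3, 3, 3.2, 3.5, 3.8, 4): AUC = 9 + 9.3 + 20.1 + 43.8 + 46.8 = 129.

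| Profile | Sample mean | Time-weighted mean | AUC | Clearance |
|---|---|---|---|---|
| A, falling | 35.5/6 = 5.92 | 4.58 | 165 | 80% |
| B, flat | 3.00 | 3.00 | 108 | 0% |
| C, worsening | 20.5/6 = 3.42 | 3.58 | 129 | −33% |

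Lower is better for the mean and the AUC, so both give the order B, C, A. By clearance the order is A, B, C. The reversal is the same for either kind of mean.

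**Unit.** Concentration multiplied by time is mmol·h/L. The stated mmol/L fits only the mean.

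**Window.** The last timed sample before 36 h is at 24 h. The next is on Day 2, with no clock time. The 24–36 h segment therefore depends on when the Day 2 sample is drawn and on an interpolation that the entry does not describe.

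**Early death.** Take rising lactate of 8, 10, 12, 14, 16 at 0, 3, 6, 12, 24 h, with death after the 6, 12 or 24 h sample. For comparison, a slowly clearing survivor D (8, 7.5, 7, 6, 5, 4) has AUC = 23.25 + 21.75 + 39 + 66 + 54 = 204.

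| Last sample before death | AUC over observed samples | AUC, last value carried to 36 h | Mean over observed time |
|---|---|---|---|
| 6 h | 27 + 33 = 60 | 60 + 30 × 12 = 420 | 60/6 = 10.0 |
| 12 h | 60 + 78 = 138 | 138 + 24 × 14 = 474 | 138/12 = 11.5 |
| 24 h | 138 + 180 = 318 | 318 + 12 × 16 = 510 | 318/24 = 13.25 |

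Summed over observed samples, death after the 6 h sample (60) scores better than all four survivors. Death after the 12 h sample (138) scores better than A and D but not B or C. Death after the 24 h sample (318) scores worse than all of them. With the last value carried forward, or with a mean over observed time, the advantage disappears in every case.

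**The case against.** The strongest reply is that the fault is mainly a label. Arms are allocated 1:1 at random, so baseline lactate is balanced in expectation, and comparing mean or AUC between arms is a valid comparison of lactate exposure. The trial compares arms and does not rank individuals. This stands, and it limits the point to what the endpoint may be called and what it can support.

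A second reply is that section 9.4 leaves tertiary analyses to the SAP, which is not at hand. That covers imputation and covariate adjustment. It does not cover the definition, which section 8.3 places in Appendix A and which is stated there in full.

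Some stronger readings are tempting but not supported:

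- A reader might infer that the AUC rewards early death as such. The protocol does not say that the AUC is summed over observed samples only, and the effect needs both that choice and a sufficiently early death. The mean, the other half of the definition, does not share the problem: 10.0 for the patient who dies after the 6 h sample against 3.00 to 6.25 for the four survivors.
- A reader might infer that mean and AUC contradict each other. A patient at 8, 6, 4, 2, 1 and then 1 at 36 h has AUC 21 + 15 + 18 + 18 + 12 = 84, better than the flat patient's 108. The mean of the five samples to 24 h is 4.2, worse than 3.0. But a time-weighted mean is 84/36 = 2.33, which agrees with the AUC, and the protocol does not say which mean is meant.
- A reader might claim a definite gain in precision from baseline adjustment. An assumed baseline to follow-up correlation of 0.5 to 0.7 would cut residual variance by its square, 25% to 49%, but the protocol gives no correlation.

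**Conclusion.** The definition does not measure clearance. It measures lactate level or exposure, and it can place a non-clearer, or even a worsening patient, ahead of one who clears 80%. That follows from the missing baseline term. The profiles are assumed and only illustrate it. The wrong AUC unit and the absent 36 h sample are plain from the text.

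The early-death point is conditional: an AUC over observed samples can, but need not, favour patients who die within roughly the first 12 h. It deserves a rule because the neighbouring enzyme AUC has one.

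The consequence is limited. The endpoint is tertiary and outside the four hierarchical hypotheses of section 9.2, so a reader should not infer any effect on the primary conclusion. Nor is lactate the only perfusion check: renal function and hemodynamic parameters are listed beside it, and excess early deaths would appear directly in the primary endpoint and in 30-day mortality.

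**What to change.** Choose one of two definitions in Appendix A and align section 8.3 with it:

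1. Rename the endpoint lactate exposure and report a time-weighted mean in mmol/L over a window that ends at a sampled time, for example 0–24 h.
2. Keep the name and compare (log) lactate between arms at the scheduled 6, 12 and 24 h samples, adjusted for baseline lactate.

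Percentage fall from baseline should not be the required form. In section 4.3 "Serum lactate > 2.0 mmol/L" is only one of four alternative perfusion signs, so some patients may enter with normal lactate, and for them a percentage fall is unstable.

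Under either option:
- Give any AUC in mmol·h/L.
- State whether time runs from randomization or from ICU admission.
- Apply one rule for deaths within the window identically to both arms, for example ranking them worst. Copying the enzyme rule would not do this, because it takes the highest value within the patient's own treatment group.

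Cost: wording in Appendix A, section 8.3 and the SAP, with no new samples. The 24–36 h segment is dropped, and ranking early deaths worst requires a rank-based analysis.
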